2.1.7 Pharmacodynamics endpoint

PD endpoint includes the urinary Hex4 level.

2.1.8 Pharmacogenetics endpoints

Pharmacogenetics endpoints will be based on baseline characteristics (Section 2.1.1).

2.1.9 Tertiary endpoints

Tertiary endpoints include:

Six-minute walk test

The 6MWT will be performed to assess functional capacity for patients who are ambulatory, defined as the ability to ambulate 40 m (approximately 130 feet) without stopping and without an assistive mobility device. The primary outcome measure of the 6MWT is the distance walked in 6 minutes recorded in meters. Test equipment and administration techniques will be standardized among the investigational sites. The percent (%) predicted value will be calculated based on the normal reference equations from Table 2 (3) (4), which cover the age range in this study. A similar approach was used by Montes et al (5). For analysis purposes, the age at each assessment will be calculated based on (assessment date - birth date + 1)/365.25. Height (which is to be assessed annually for patients with age ≥ 18 years and every 3 months for patients with age < 18 years) will be based on the most recent valid value at or prior to the assessment date.

Table 2 - Equations for calculating reference value for percent predicted total distance walked in 6MWT

Reference	Age at baseline	Gender	Equation
(3)	≥ 18 years	Male and Female	$868.8 - 2.99 * \text{age} - 74.7 * \text{sex}$
(4)	< 18 years	Male	$196.72 + 39.81 * \text{age} - 1.36 * \text{age}^2 + 132.28 * \text{height}$
	< 18 years	Female	$188.61 + 51.50 * \text{age} - 1.86 * \text{age}^2 + 86.10 * \text{height}$

Age in years; sex = 0 if male and sex = 1 if female; height in meters.

Additional information, including the amount of time walked (to quantify endurance, as all patients may not complete the full 6-minute walk), as well as the use and change from baseline in

assistive mobility devices (including straight cane, wide-based cane, one crutch, two crutches, standard walker, rolling walker, orthotics and other) will also be reported.

Pulmonary function testing

The PFT will include the assessment of FVC, forced expiratory volume in the first second of the FVC maneuver (FEV1), maximal inspiratory pressure (MIP), maximal expiratory pressure (MEP), and peak expiratory flow in the upright and supine positions. Pulmonary function tests are not required for young patients unable to reliably undergo testing or for patients who are invasively ventilated, but missing assessments must be documented for analysis and potential impact on the study results.

FVC will be reported in absolute value in liters. The FVC (% predicted) value is defined as $100^* (\text{actual FVC measurement}/\text{predicted value of FVC})$. The Quanjer GLI-2012 regression equations and lookup tables (1) are used to calculate predicted values of FVC. Predicted values of FVC are functions of sex, age in years (3-95 years), height in cm, and ethnic group (Whites, African Americans, South East Asians, North East Asians and for Other ethnic groups or people of mixed descent). FVC is predicted according to the following equation:

$$M = \exp(a_0 + a_1 \cdot \ln(\text{Height}) + a_2 \cdot \ln(\text{Age}) + a_3 \cdot \text{black} + a_4 \cdot \text{NEAsia} + a_5 \cdot \text{SEAsia} + a_6 \cdot \text{Other} + \text{Mspline})$$

Where

black = 1 if a subject is African American, otherwise = 0

NEAsia = 1 if a subject is from North East Asia, otherwise = 0

SEAsia = 1 if a subject is from South East Asia, otherwise = 0

Other = 1 if subject is 'other ethnic group' or mixed ethnicity, otherwise = 0

Coefficients a(n) depend on sex and are given by lookup table

Mspline is age-varying coefficients, given by lookup table for each type of sex

For the analysis purpose, the age will be calculated based on (assessment date - birth date + 1)/365.25. Height will be based on the most recent valid value at or prior to the assessment date.

The percent predicted values for MIP and MEP will be calculated (6, 7). The normal reference values used for percent predicted calculation will be dependent on each patient's age, gender, and weight (Table 3). For each patient, the same equations used for the baseline will be used to calculate the predicted values (eg, if a patient started at ≤ 17 years of age and turns 18 during the study, he/she will still use the pediatric formula after turning to 18). For analysis purposes, the age will be calculated based on (assessment date - birth date + 1)/365.25. Weight for age < 18 will be based on the most recent valid value at or prior to the assessment date. The percent predicted value is defined as $(\text{absolute measurement}/\text{normal reference value}) * 100$. Since the reference

values will be available only for patients of age 7 years or older, the percent predicted MIP and MEP will not be derived for patients aged <7.

Table 3 - Reference equations for predicted value of MEP and MIP

Test/Age at baseline	Male	Female
MEP		
≥18 years old (6)	174 – 0.83 * age	131 – 0.86 * age
7–17 years old (7)	35 + 5.5 * age	24 + 4.8 * age
MIP		
≥18 years old (6)	120 – 0.41 * age	108 – 0.61 * age
7–17 years old (7)	44.5 + 0.75 * weight	40 + 0.57 * weight

Age in years; weight in kg.

All PFTs will be reported centrally from Biomedical Systems (BMS) following pulmonary software specification and user requirement (2).

Ventilator use diary

The Investigator will provide a respiratory diary to the patient (and/or the patient's parent[s]/legal guardian[s]) to record the daily use (if any) of mechanical ventilation (including both invasive and non-invasive) at daytime and nighttime. The date the patient first became dependent on invasive ventilator, as well as the reasons for first ventilator use will be collected and results will be recorded in the e-CRF. If the patient requires mechanical invasive or non-invasive ventilator support during the study, the start date, stop date, and reasons for each episode of continuous mechanical ventilator support will be collected. Invasive ventilation is defined as mechanical ventilatory support applied with the use of an endotracheal tube or tracheostomy, and noninvasive ventilation is defined as ventilatory support applied without the use of an endotracheal tube, i.e., no invasion of the airway. On a bi-weekly basis, the average number of hours of ventilator use/day will be calculated by the Investigator based on the ventilator use diary and data recorded until (1) ventilator support is no longer needed; (2) patient death; or (3) end of study (whichever occurs first). The date and reason that ventilator use is no longer needed will be recorded. The daily ventilator use diary is only required to be completed for patients using ventilator support.

If the patient requires any invasive or non-invasive mechanical ventilation (excluding planned ventilatory support less than 3 days duration for a planned surgical procedure), the Investigator will describe the events leading up to the mechanical ventilation using the ventilator use form/log in the e-CRF.

PedsQL Generic Core Scale questionnaire

The PedsQL Generic Core Scales is a general HRQOL tool. If patients are unable to complete this assessment, a parent proxy form will be used. During the treatment period, the assessment will be completed before IMP infusion if possible, and the patients will continue on the age-

specific assessment they first completed at screening/baseline, even if they exceed the age range for that specific tool over the study duration. The 23-item PedsQL Generic Core Scale encompasses 4 subscales including a patient's health and activities, feelings, problems with school, and how the patient gets along with others. Items are evaluated on a 5 point Likert scale with 0 = never, 1 = almost never, 2 = sometimes, 3 = often, and 4 = almost always, and the data from the questionnaire will be collected.

The 4 Multidimensional Scales and 3 Summary Scores are:

- Scales
 - Physical Functioning (8 items)
 - Emotional Functioning (5 items)
 - Social Functioning (5 items)
 - School Functioning (5 items)
- Summary Score
 - Total Scale Score (23 items)
 - Physical Health Summary Score (8 items)
 - Psychosocial Health Summary Score (15 items)

Items are reverse scored and linearly transformed to a 0 - 100 scale, so that higher scores indicate better HRQOL. To reverse score, transform the scale items to 0 - 100 as follows: 0 = 100, 1 = 75, 2 = 50, 3 = 25, and 4 = 0. To create scale scores, the mean is computed by totaling the item scores and dividing by the number of items answered. This direct linear transformation does not affect the measurement properties of the scales, and is computed for ease of interpretation so that scores near 0 indicate poorer HRQOL and scores near 100 indicate better HRQOL. Scale scores are computed as the sum of the items divided by the number of items answered (this accounts for missing data). If more than 50% of the items in the scale are missing, the Scale score is not computed.

When examining the total scale, scores of 4.4 and 4.5 are considered to be minimal clinically meaningful differences on the child self-report and parent-proxy report, respectively.

Parents, children (ages 8 - 12 years), and adolescents (ages 13 - 18 years) may self-administer the PedsQL Generic Core Scale after instructions from the administrator. For younger children (ages 5 - 7 years) or if the child or adolescent is unable to self-administer the PedsQL Generic Core Scale (eg, due to illness, fatigue, reading difficulties), the measure should be read aloud.

The PedsQL Infant Scales version consists of the following 5 domains: (1) physical functioning, (2) physical symptoms, (3) emotional functioning, (4) social functioning, and (5) cognitive functioning. It includes formats for typically developing children 1 to 24 months old (parent-proxy report). The format, instructions, response scale, and scoring methods of the Infant Scales are identical to those of the Generic Core Scales.

PedsQL Pediatric Pain Questionnaire

The 3-item PedsQL Pediatric Pain Questionnaire comprises:

- Present Pain;
- Worst Pain;
- The third item refers to the localisation of pain and is not scored.

10 cm (100 mm) VAS scales from 0 (Not hurting/No discomfort/No pain) to 10 (100) (Hurting a whole lot/Very uncomfortable/Severe pain).

The format, instructions, Likert response scale, and scoring method are identical to the PedsQL 4.0 Generic Core Scales, with higher scores indicating higher pain intensity. Present pain and worst pain are scored separately. The score is based on line length to the nearest 0.5 cm (5 mm). There is no imputation process since these are single item VAS scales. The instructions for the standard version ask how much of a problem each item has been during the past one month. In this study, the PedsQL Pediatric pain Questionnaire will be applied to participants >5 years of age.

Observer reported pain visual analogue scale

The Observational Visual Analogue Score (VAS-OBS, range 0-10) is a tool developed to measure subjective phenomena like pain. It usually consists of a 10-cm line, either vertical or horizontal, anchored at the ends by labels such as “no pain” and “worst possible pain.” Observers estimate the level of perceived pain by putting a mark on the line. An observer uses the VAS to rate the intensity of the pain experienced by children. In this study, the VAS-OBS will be applied to all participants.

Bayley Scale of Infant and Toddler Development, Third Edition

The Bayley-III is an individually administered instrument that assesses the developmental functioning of infants and young children between 1 month and 42 months of age. For this study, the Cognitive Scale and Motor Scale will be utilized. The Cognitive Scale assesses how a child thinks, responds and learns about the world. The Motor Scale is comprised of two subtests: the Fine Motor subtest and the Gross Motor subtest. The Fine Motor subtest assesses how well a child can use his or her hands and fingers to perform activities. The Gross Motor subscale assesses how well a child can move his or her body. Normative data are available for the Bayley-III from 1 month to 42 months of age and were derived from a sample of US infants and children in 2004. Raw scores, scaled scores, and age equivalent scores will be reported for the Cognitive, Fine Motor, and Gross Motor subtests. Composite scores with percentile rank and confidence intervals will be reported for the Cognitive Scale and the Motor Scale (a composite of the Fine Motor and Gross Motor subtests). Test results will be centrally scored by a trained assessor.

Leiter International Performance Scale, Third Edition

The Leiter-3 will be administered by a trained assessor to assess intellectual ability. The Leiter Scale was designed as a nonverbal measure of intellectual function, memory and attention for individuals who could not be validly assessed with standard intelligence tests.

The Leiter-3 consists of two groups of subtests, the Cognitive Battery and the Attention/Memory Battery. Nonverbal Intelligence will be used in this study to estimate global intellectual ability. The first four subtests of the Cognitive Battery are compiled to assess Nonverbal Intelligence with a Nonverbal IQ Composite score. These subtests are: Figure Ground, Form Completion, Sequential Order, and Classification-Analogies. The fifth subtest (Visual Patterns) is an optional subtest, which may be administered if one of the four subtests is compromised. Raw and scaled scores will be reported for each administered subtest in addition to the Nonverbal IQ Composite score, corresponding percentile rank, and 95% Confidence Interval.

The Leiter-3 will be administered to patients starting at the last assessment of the Bayley-III Cognitive Scale prior to the patient reaching 42 months of age and then test results will be centrally scored by a trained assessor.

In case the developmental level of an individual patient is below the level required for the Leiter-3 Scale assessment, the patients should be assessed by the Bayley-III regardless of the patient's age.

Hearing Testing

Hearing will be assessed using both Audiogram and Brainstem auditory evoked potentials/responses (BAEPs/BAERs).

- Audiogram: [Table 4](#) summarizes a list of commonly available hearing tests appropriate for infants and children of various ages. Abnormal hearing tests should be confirmed by more than one method, and should be correlated with the presence or absence of middle ear effusion. Results of the hearing testing will be collected.

Table 4 - Hearing assessments appropriate for age **Auditory test** **Developmental age of child**

Auditory test	Developmental age of child
Otoacoustic emission testing	All ages
Conditioned-oriented responses	9 months to 2.5 years
Visual reinforcement audiometry	9 months to 2.5 years
Play audiometry	2.5 years to 4 years
Conventional audiometry	4 years and older

Source: Cunningham, 2003 (49)

- BAEPs/BAERs will be recorded in order to measure the functioning of the auditory nerve and auditory pathways in the brainstem, thus aiding in the assessment of potential hearing loss in study participants. Since recording of BAEPs/BAERs may require sedation in young children which could pose unacceptable risks to patients who have significant cardiopulmonary compromise, BAEPs/BAERs should only be performed at the discretion of the Investigator. Missing assessments must be documented for analysis and potential impact on the study results. If clinically significant changes in hearing as compared to baseline results are noted, the changes will be documented as AEs. Clinical significance is defined as any variation in hearing tests that has medical relevance and may result in an alteration in medical care. The Investigator will continue to monitor the patient until the

parameter returns to baseline or until the Investigator determines that follow-up is no longer medically necessary.

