7 SELECTION OF PATIENTS

7.1 INCLUSION CRITERIA

- I 01. The patient who has reached legal age of majority as defined by local regulation or the patient's legal guardian(s) must provide signed informed consent prior to any study-related procedures being performed. If the patient is legally minor per local regulations, assent shall be obtained from the patient, if applicable.
- I 02. The patient must have a documented GAA deficiency from blood, skin or muscle tissue for confirmation of diagnosis of IOPD.
- I 03. The patient is aged <18 years old.
- I 04. The patient has cardiomyopathy at the time of diagnosis: ie, left ventricular mass index (LVMI) equivalent to mean age specific LVMI plus 2 standard deviations as published by Vogel (19).
- I 05. The patient has been receiving a stable dose of alglucosidase alfa regularly for a minimum of 6 months immediately prior to study entry.

For patients participating in Stage 1: Clinical Decliners Dose Cohort 1 & 2

- I 06. The patient has evidence of clinical decline in at least 1 of the following parameters related to Pompe Disease and NOT related to intercurrent illness as assessed by the Investigator. To document decline, at least 2 recent and consecutive assessments prior to study entry, not less than 2 weeks apart, are required, in addition to at least 1 previous assessment prior to onset of decline:
 - *Respiratory Function*
New development or worsening of respiratory failure requiring the use or increased use of ventilatory assistance (invasive or non-invasive). Ventilatory assistance must have been required for at least 4 weeks prior to study enrollment,

OR

- *Motor Skills*
For patients ≤ 2 years of age at study entry, failure to acquire at least 2 new age appropriate gross motor milestones at least 6 months prior to study enrollment, eg:
 - Turning head side to side (supine)
 - Grasping small objects with hands
 - Transferring objects from hand to hand
 - Holding head upright with body supported
 - Rolling (supine to prone or prone to supine)

- Sitting (supported or unsupported)
- Transition in and out of sitting (lying to sitting, sitting to quadruped)
- Crawling
- Pull to stand
- Walking (with support, ie, cruising, or independently)
- Squatting (stand to squat, squat to stand),
- Walking up stairs (with assistance or independently)

OR

For patients >2 years of age at study entry, documented worsening of muscle weakness demonstrated by a loss of one of the following:

- Independent ring

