9.3.3.2 Six-minute walk test

The 6MWT (34) will be performed at the time points specified in [Section 1.2](#) to assess functional capacity for patients that are ambulatory, defined as the ability to ambulate 40m (approximately 130 feet) without stopping and without an assistive device. The 6MWT was originally developed as a global assessment of cardiac, respiratory, circulatory, and muscular capacity for adults (34). The 6MWT utilization has been expanded to neuromuscular disease research with adults and children, including studies of laronidase in mucopolysaccharidosis type-I (MPS-I) (35), idursulfase in mucopolysaccharidosis type II (36), and has proved safe, reliable and feasible in Duchenne muscular dystrophy (37). For administration to children, the guidelines proposed by the ATS have been modified to include accommodation to children's instructional needs, strategies for ensuring motivation, and techniques for promoting safety (37). Testing equipment and administration techniques will be standardized among investigational sites.

For the purpose of stabilization and if deemed necessary by the Investigator, the participant may use a walking device, such as cane or walker, during the assessment. If such a device is used during the assessment or there is a change in device use during the trial, this must be recorded in the e-CRF.

During the treatment period, the assessment will be completed before IMP infusion. The distance (in meters) will be recorded and the corresponding percent predicted value will be calculated (38). In addition, data will be collected for pre- versus post-test changes in heart rate.

See the study-specific functional outcome manual for further details.

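### SAP Table 2 fixes the 6MWT equation by age at baseline but enters current age, so after 18 an unchanged distance gives a rising percent predicted

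*SAP*

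**What the plan says.** SAP 2.1.9 (Six-minute walk test) makes distance in metres the main measure and adds a percent predicted value from the equations in Table 2, "which cover the age range in this study". Protocol 9.3.3.2 also requires it: "the corresponding percent predicted value will be calculated".

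Two different ages enter the calculation:

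- **Choice of row.** The selecting column of Table 2 is headed "Age at baseline", with one row for 18 and over and two, by sex, for under 18.
- **Age put into the equation.** "For analysis purposes, the age at each assessment will be calculated based on" (assessment date − birth date + 1)/365.25. Height is the most recent valid value.

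Protocol 7.1, criterion I 03, sets the entry limit: "The patient is aged <18 years old". At study entry, then, every eligible patient falls in a paediatric row. The 6MWT text has no rule for a patient who later passes 18, although the same paragraph gives a height schedule for patients aged 18 or more. For MIP and MEP, the same section does say that the paediatric formula is kept after 18.

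**The concern.** Percent predicted is meant to take age out of the comparison. The two paediatric equations are quadratics that peak in the mid-teens and then fall ever faster. Once a patient is past 18, the equation gives a shrinking normal distance, so a stable walk looks like improvement and a modest loss can look like stability. In a progressive disease that is the unhelpful direction of error. In the extension all continuing patients receive avalglucosidase alfa (Protocol 8.1.2), so there is no concurrent arm carrying the same artefact. SAP 2.4.10 summarises changes from baseline at every later visit, and with about 20 patients in all one or two adolescents could move a cohort mean.

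**Working it through.** The documents give no worked 6MWT value, so there is no figure to reproduce. I evaluated Table 2 directly.

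**Inputs from the documents** (age in years, height in metres)
- Male under 18: 196.72 + 39.81·age − 1.36·age² + 132.28·height
- Female under 18: 188.61 + 51.50·age − 1.86·age² + 86.10·height
- Adult: 868.8 − 2.99·age − 74.7·sex (female = 1)
- Week 25 is Day 169 and Week 145 is Day 1009 (SAP Table 5): 168/365.25 = 0.46 and 1008/365.25 = 2.76 years after Day 1
- Week 371 (Protocol 10.1.4.1): 370 × 7 = 2590 days, or 7.09 years

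**Assumptions, not in the documents:** constant distance 400 m; fixed height 1.70 m (male) and 1.60 m (female).

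**Step 1. Shape.** The references peak at 39.81/(2 × 1.36) = 14.6 years (male) and 51.50/(2 × 1.86) = 13.8 years (female). The slope at 18 is 39.81 − 2.72 × 18 = −9.2 m/year (male) and 51.50 − 3.72 × 18 = −15.5 m/year (female), and it steepens later. Growth would have to be 9.15/132.28 = 6.9 cm/year or 15.46/86.10 = 18.0 cm/year to cancel it at 18, so updating height does not help.

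**Step 2. Who is affected.** Passing 18 by Week 145 needs entry at 18 − 2.76 = 15.2 years or older; by Week 371, 18 − 7.09 = 10.9 years or older.

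**Step 3. Size at Week 145.** Percent predicted is 100 × 400/reference. The post-18 error is the value as written minus the value with age held at 18.0. For the girl entering at 16.0:
- at entry: 188.61 + 824.00 − 476.16 + 137.76 = 674.2 m, 59.3%
- at 18.0: 188.61 + 927.00 − 602.64 + 137.76 = 650.7 m, 61.5%
- at 18.76: 188.61 + 966.14 − 654.60 + 137.76 = 637.9 m, 62.7%

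Of her 3.4-point rise, only 62.7 − 61.5 = 1.2 points arise after 18.

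| Entry | Reference at entry, at 18.0, at Week 145 (m) | % at entry | % at Week 145 as written | % with age held at 18.0 | Post-18 error (points) |
|---|---|---|---|---|---|
| Boy 16.0 | 710.4, 697.5, 689.8 | 56.3 | 58.0 | 57.3 | 0.6 |
| Girl 16.0 | 674.2, 650.7, 637.9 | 59.3 | 62.7 | 61.5 | 1.2 |
| Boy 17.9 | 698.4, 697.5, 663.6 | 57.3 | 60.3 | 57.3 | 2.9 |
| Girl 17.9 | 652.3, 650.7, 596.5 | 61.3 | 67.1 | 61.5 | 5.6 |

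Errors come from unrounded percentages; subtracting the rounded ones gives 0.7 and 3.0 for the boys.

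**Step 4. Sensitivity.** The error in points scales with the distance assumed. The relative error does not: 697.5/689.8 to 697.5/663.6 is 1.1% to 5.1% (boys), and 650.7/637.9 to 650.7/596.5 is 2.0% to 9.1% (girls). For entry at 17.9, heights of 1.50 to 1.80 m give 2.8 to 3.2 points (male), and 1.45 to 1.70 m give 5.4 to 5.8 points (female).

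**Step 5. Other time points.** At Week 25 the largest whole change among these ages is the girl entering at 17.9: 652.3 to 644.9 m, 61.3% to 62.0%, or 0.7 points. If the rule were carried to Week 371, references for entry at 16.0 and 17.9 would be 615.7 and 567.1 m (boys) and 523.8 and 451.7 m (girls). Post-18 errors would then be about 8 to 13 points (boys) and 15 to 27 points (girls).

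**The case against.** The case for leaving the plan alone is substantial, and most of it stands as a limit on reach.

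- **Little rests on percent predicted.** Metres are the stated main measure, and the ADA plots (SAP 2.4.5) and the correlation analysis (2.4.10.1) use distance. No test uses 6MWT percent predicted. A reader might infer that the missing control arm hides the artefact completely. It does not: an unchanged distance in metres would expose it.
- **The large figures are not outputs of this SAP.** It describes follow-up of up to 3 years (Section 3) and its efficacy windows stop at Week 145 (Table 5). Only the protocol reaches Week 371, and that period can end earlier on approval.
- **Few patients may qualify.** They must be old enough, walk 40 m unaided and, for the descriptive summary, complete the six minutes (SAP 2.4.8).
- **The adult row is not strictly dead.** A reader might infer from I 03 that it can never apply. But SAP 1.5 and 2.1.1 reset baseline for Cohort 3 patients who switch to avalglucosidase alfa. Someone entering at about 18 − 0.46 = 17.54 or older could be 18 at that second baseline.
- **Keeping the baseline equation is an SAP convention.** It is explicit for MIP and MEP, and it does not always flatter the drug: the paediatric MEP equations rise with age, so an unchanged MEP gives a falling percent predicted.
- **The row label concerns baseline age.** It does not state the range over which the equation is valid, and the cited source is not available here.

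What does not stand is the conclusion that the rule is therefore sound. The convention explains why the paediatric equation is kept; it does not make a reference that falls at an increasing rate after 18 a sensible normal value.

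**Conclusion.** The defect holds for ambulatory patients who enter under 18, pass 18 and stay on the paediatric row. It is minor. Its size at Week 145 is about 0.6 to 2.9 points (boys) and 1.2 to 5.6 points (girls) for entry between 16.0 and 17.9, under the assumed 400 m and heights. How many patients it touches is unknown.

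Three stronger readings should be resisted:

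- **That every patient's percent predicted is inflated.** Before the peak, an unchanged distance gives a falling percent predicted, as age adjustment intends.
- **That all of the drift in an adolescent is error.** The decline from about 14 to 18 lies within the labelled range and is left as it is.
- **That the primary analysis or the safety conclusions are at risk.** The primary endpoint is safety, and the Week 25 effect is negligible.

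**What to change.** Add one sentence to SAP 2.1.9: for patients under 18 at study entry, use the paediatric equation throughout, taking the PAP baseline to choose the row (also for Cohort 3 switchers), and enter age 18.0 at any assessment after the 18th birthday, with height still updated. The cost is that percent predicted after 18 rests on the age-18 reference, and that 6MWT then has an age cap which MIP and MEP lack.

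Do not switch to the adult row at 18. At the assumed heights the reference would jump from 697.5 to 815.0 m (male) and from 650.7 to 740.3 m (female), so 400 m would drop from 57.3% to 49.1% and from 61.5% to 54.0%. That replaces a drift with a step. Nothing need change for distance in metres. If a later SAP covers follow-up to Week 371, it should carry the same sentence, because that is where the error would grow large.
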